## 9.4 STATISTICAL ANALYSES

### 9.4.1 GENERAL APPROACH

Baseline demographic and clinical characteristics will be presented using descriptive statistics, as applicable. Unadjusted outcome summary statistics will be described for each randomized group. Continuous variables will be summarized by mean (standard deviation), median (25th, 75th) percentiles, and range. Categorical variables will be summarized by percentage.

The primary analysis dataset consists of all randomized participants and will be analyzed using intention-to-treat (ITT) principles such that each subject is analyzed based on their allocated arm. Mortality and dropout may occur, and subjects will be analyzed as described in 9.4.2 and 9.4.3.

A secondary analysis approach may consider a per-protocol analysis, analyzing those participants who completed study procedures without major protocol violations. The per-protocol analysis definition will be finalized prior to database lock and data analysis. The ITT analysis will be considered primary.

### 9.4.2 ANALYSIS OF THE PRIMARY EFFICACY ENDPOINT(S)

The primary outcome is hemoglobin measured repeatedly on subjects at ICU discharge, hospital discharge, and 1 month and 3 months. The longitudinal trajectory of hemoglobin will be analyzed with a LMM. The primary parameter of interest is a treatment group by time interaction to estimate the effect of treatment at each follow up time-point. The treatment effect on 1 month hemoglobin is the primary outcome; other time-points will reflect secondary outcomes. As the functional form of hemoglobin over time is unknown, a discrete time representation will be used. The model will adjust for pre-randomization hemoglobin, age, sex, anemia etiology, and medical vs surgical ICU setting to reduce residual variation and improve precision of the estimated treatment effect.

Dropout or non-response including skipped study visit and death represent two forms of missing data. Dropout or non-response unrelated to death at ICU discharge and hospital discharge is expected to be negligible but could occur with withdrawal of consent. We assume dropout (unrelated to death) while in the ICU is missing completely at random (MCAR); subjects withdrawing consent prior to observation of hemoglobin outcome at ICU discharge will be excluded from the analysis. Those dropping out after ICU discharge are assumed missing at random (MAR) with missingness possibly related to adjustment covariates, arm, or prior observed hemoglobin values. Analyses using LMM assume dropout, nonresponse, or skipped visits are MAR.

We anticipate up to 10% ICU mortality (despite exclusion of those not expected to survive hospitalization); such subjects will not have observed hemoglobin outcomes. We also anticipate additional post-ICU discharge mortality. In the primary analysis, we assume missing data due to death is MAR. Those with ICU mortality will have ICU discharge hemoglobin multiply imputed under the MAR assumption. Thereafter, LMMs assume additional missing data at other times are MAR. In secondary approaches to the analysis of hemoglobin, we use a worst-case imputation approach, to impute hemoglobins as the worst possible outcome following death. After imputation, if residuals are not reasonably normally distributed, a generalized linear mixed effects proportional odds model will be used or individual timepoints may be assessed by Wilcoxon rank-sum test without covariate adjustment.

In the primary analysis, the point estimate, 95% confidence interval, and p-value will be reported from the LMM for the 1 month hemoglobin comparison. A point estimate in the direction favoring higher hemoglobin for the intervention arm

and two-sided p-value<0.05 will reject the null hypothesis of no treatment benefit in favor of the conclusion that intervention improves 1 month hemoglobin.

#### 9.4.3 ANALYSIS OF THE SECONDARY ENDPOINT(S)

Secondary and exploratory endpoints (besides hemoglobin at 3 months) include EQ-5D [Time frame: hospital discharge, 1 month, and 3 months post-hospitalization], PROMIS-Fatigue [Time frame: hospital discharge, 1 month, and 3 months post-hospitalization], 6-minute walk distance, activity monitoring (i.e. daily step counts, daily energy expenditure), and activities of daily living survey [Time frame: 1 and 3-months post-hospitalization], MoCA-BLIND [Time frame: 1 and 3-months post-hospitalization], HADS and IES-R [Time frame: 1 and 3-months post-hospitalization].

**Activity Monitoring:** During the initial consent process for the study, subjects will be given the option to also consent for activity monitoring at 1- and 3-months post-hospitalization. Activity monitors (AMs) are wearable devices (Actigraph) that will be provided to participants by mail. Participants will be asked to wear these monitors to measure physical activity and sedentary behavior in the free-living environment. The monitors will be worn over 4 consecutive days, which will occur during the 1- and 3-month assessment intervals. Devices will be distributed to patients either in-person during their 1- and 3-month appointments or delivered via mail. Participants will be given a pre-paid envelope to mail the activity monitors back after 4 consecutive days of wear. A valid AM hour is defined as  $\leq 30$  minutes of consecutive 'zero' values (no activity) and a valid AM day is defined as  $\geq 10$  wear hours per day. Subjects will be asked to repeat wearing the AM if a data collection contains  $\leq 2$  valid days across 4 days, or if the AM has malfunctioned. AMs are attached with straps worn on the non-dominant wrist. All activity monitors can be worn comfortably under or over clothing. The activity monitors are to be put on in the morning upon waking and removed at night before bed. The sensors are not waterproof and will be removed for bathing and swimming. The risks from wearing an AM are no different than those normally encountered in the free-living environment. Instructions for participants are provided in Appendix 3.

Analyses will use Wilcoxon rank-sum tests to compare the distribution of each outcome between groups at each timepoint since assumptions including normality of residuals are not expected to be satisfied for these outcomes. Additional, when applicable, a cutpoint defining a clinically actionable adverse outcome may be defined, for example, defining depression by HADS-Depression  $\geq 8$ . Binary outcomes will be summarized as proportion and compared by randomized arm using a Chi-square test. Death and dropout will be assumed MAR in the primary approach and multiple imputation will be used to impute missing values. Analyses will be conducted on each imputed dataset and results combined to reflect uncertainty due to missing data. An additional analysis will consider a worst-value imputation for mortality, assigning death the worst possible outcome.

Mortality and readmission through 1 year post-discharge will be described by randomized arm using cumulative incidence estimates, censoring subjects at last known contact with the Mayo medical system when status is unknown at 1 year. Inferential analyses will use log-rank tests and Gray's test for mortality and readmission outcomes, respectively.

Since the goal is to provide robust data for further clinical trial evaluation, secondary and exploratory outcomes will be assessed without adjustment for multiplicity, with conclusions from each based on a two-sided alpha level 0.05 statistical test.

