## 1.2 SCHEMA

## 1.3 SCHEDULE OF ACTIVITIES (SOA)

Procedures	Enrollment/ Baseline Study day 1	Daily visits throughout hospitalization	Hospital Discharge	1-month post- hospitalization +/- 7 days	3-months post- hospitalization +/- 14 days	12-months post- hospitalization EMR review
Informed consent	X					
Demographics	X					
Medical history	X					
Randomization	X					
Administer study intervention	X					
Vital signs- (BP, HR, RR, O2 sat)	X					
Height	X					
Weight	X		X			
Pregnancy test if needed	X					
Anemia labs a	X	X	X	X	X	
Platelet count d	X		X			
White blood cell count d	X		X			
Creatinine d	X		X			
Functional outcome assessment b	X		X	X	X	
Con medication review c	X	X				
Fluid balance	X		X			
RBC transfusions documented	X	X	X	X	X	
Daily phlebotomies for labs (excluding RMGs)		X	X			
Fatigue assessment			X	X	X	
AE review and evaluation	X	X	X	X	X	
Research Samples e	X			X	X	
Hospital readmissions documentation				X	X	X
All cause mortality status						X
Complete Case Report Forms	X	X	X	X	X	X

a. Hemoglobin, ferritin, and transferrin saturation will be obtained for all patients at enrollment, hospital discharge, 1-month, and 3-months post-hospitalization. Other anemia labs to be reported at these and other timepoints include, if available Hemoglobin, MCV, RDW, ferritin, iron, transferrin saturation, reticulocyte hemoglobin, absolute reticulocyte count; record all values available recognizing that not all non-hemoglobin values will be available at each interval.

b. Functional outcomes according to the Core Outcome Measurement Set will be obtained in the following fashion: Enrollment – ADL survey (by patient or proxy); at Hospital discharge – EQ-5D, PROMIS-FATIGUE; at 1-month and 3-months – EQ-5D, PROMIS-FATIGUE, 6MWD, ADL Survey, MoCA-BLIND, HADS, IES-R, activity monitoring (optional study component).

c. Concomitant meds review to include y/n for antiplatelet agents (i.e. aspirin, clopidogrel), anticoagulants (i.e. heparin, warfarin, direct oral anticoagulants, low molecular weight heparins), iron, and erythropoiesis stimulating agent use (i.e. darbepoetin, EPO). Daily visits only need to report if they received iron or EPO/darbepoetin.

d. Platelets, WBC and Creatinine will be collected if done as standard of care. Baseline results used should be from within 24 hrs prior to enrollment. Hospital discharge results used should be the closest to discharge up to 72 hours prior.

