Patients satisfying inclusion/exclusion criteria, or their legal proxies, will be approached by trained study coordinators for written informed consent. Participants will be randomized 1:1 to active intervention vs. standard care using a stratified permuted block design by anemia etiology (iron-responsive or not) and ICU admission indication (surgical vs. non-surgical). The intervention arm is multi-faceted with 3 primary components: 1) **Optimized phlebotomy**, defined by minimal volume draws (i.e. 0.1-2 ml vs. standard 3-10 ml per laboratory order) and closed-loop blood sampling (eliminates 10 ml waste volume per draw), all performed by a dedicated phlebotomy team independent from the treatment team; 2) **Decision support aids**, including visual and electronic alerts reminding the care team to minimize non-essential laboratory testing and mitigate patient-specific bleeding risk (e.g. stress ulcer prophylaxis in high-risk patients); and 3) **Pharmacologic anemia treatment** (given immediately following enrollment when hemoglobin first observed <10 g/dL) targeted to 2 broad groups: 1) anemias responsive to iron supplementation alone (i.e. acute blood loss, true iron deficiency [i.e. ferritin <100 ng/ml, transferrin saturation < 20%]), and 2) anemias requiring erythropoietic stimulation (e.g. anemia of inflammation, anemia of renal disease). Etiology of anemia will be determined immediately prior to randomization upon review of laboratory values (i.e. iron studies) and clinical history (i.e. admission diagnoses, surgery/acute blood loss) with treatment decisions adjudicated pre-randomization by the PI or Co-I's. Subjects then randomized to the intervention arm will receive pharmacologic anemia treatment in accordance with their anemia etiology. Patients with anemias responsive to iron supplementation will receive a single total dose infusion (1000 mg) of intravenous (IV) iron dextran. Patients with anemias requiring erythropoietic stimulation will receive a single dose of 40,000 units of subcutaneous EPO, which will be immediately preceded by 1000 mg of IV iron dextran to replenish usable iron stores if the ferritin level is < 1000 ng/ml. All patients randomized to the intervention group will receive

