### 6.3 MEASURES TO MINIMIZE BIAS: RANDOMIZATION AND BLINDING

Participants will be randomized 1:1 to active intervention vs. standard of care using a stratified permuted block design by anemia etiology (iron responsive vs. not) and ICU admission indication (surgical vs. non-surgical). Randomization will occur electronically using the REDCap randomization module. Randomization lists will be developed by the study statisticians and uploaded directly to REDCap. Study staff involved in patient care are unable to access randomization lists in advance and therefore are unlikely to predict future randomization/assignment. Clinicians and subjects will not be blinded to study interventions. However, all data analysts will be blinded to treatment allocation while the study is ongoing.

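### Optional improvement, secondary functional outcomes only: the Wilcoxon tests in 9.4.3 are valid but leave out both randomisation factors; adjusting for them gains roughly 1 to 4 power points if they are modestly prognostic and costs about half a point or less if they are not

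*Combined protocol and SAP*

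**What the plan says.** Section 9.4.3 on the functional outcomes: "Analyses will use Wilcoxon rank-sum tests to compare the distribution of each outcome between groups at each timepoint". The reason given is that normal residuals are not expected. Missing values are multiply imputed under MAR: "Analyses will be conducted on each imputed dataset and results combined to reflect uncertainty due to missing data". A further analysis covers deaths: "An additional analysis will consider a worst-value imputation for mortality, assigning death the worst possible outcome". The section names no strata, covariates, imputation-model variables, pooled quantity or between-arm effect measure for these outcomes. Each test is at two-sided 0.05 without multiplicity adjustment.

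Section 6.3 randomises 1:1 "using a stratified permuted block design by anemia etiology (iron responsive vs. not) and ICU admission indication (surgical vs. non-surgical"). Section 4.1 fixes the first factor before allocation: "Etiology of anemia will be determined immediately prior to randomization upon review of laboratory values". The primary model in Section 9.4.2 adjusts for pre-randomisation hemoglobin, age, sex, "anemia etiology, and medical vs surgical ICU setting to reduce residual variation".

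The statistical considerations in Section 4.1 are wider than 9.4.3. They allow either proportional-odds models or the Wilcoxon test for functional outcomes, but list no covariates for them.

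The ADL survey is taken at enrollment from patient or proxy (Section 1.3, footnote b) and again at 1 and 3 months. Section 9.4.3 does not use the enrollment value. In the schedule, the survey, randomisation and study treatment share one column, "Enrollment/ Baseline Study day 1".

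**The concern.** The plan uses its design factors for hemoglobin but not for functional recovery, which is the other half of its stated hypothesis. Stratified allocation balances the arms on the two factors, so between-stratum variation largely drops out of the arm comparison. The Wilcoxon variance still counts that variation. If the factors are prognostic, the test rejects less often than 5% under the null and loses some power.

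There is also a reporting gap. Wilcoxon p-values have no direct Rubin's-rules form, and no between-arm estimate with a confidence interval is planned for these outcomes, whereas Section 9.4.2 plans one for hemoglobin. Section 9.4.3 gives data for further trials as the aim, and the next trial would need an effect size.

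**Working it through.** **Inputs from the documents.** 37 per arm analysed, SD 1.5 g/dL, difference 1.0 g/dL, R² = 0.25 for all hemoglobin covariates together, 25% dropout, 100 enrolled (Section 9.2); two binary stratification factors (Section 6.3).

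**Assumed, because the documents give no value.** R² of the two factors for a functional outcome: 0, 0.05 or 0.10. Shift between arms: 0.5 to 0.68 SD. Blocks of 4. Functional score on a 0–21 scale. The 0.25 in Section 9.2 is not borrowed: it concerns hemoglobin and five covariates.

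**1. The plan's own figures.** Noncentrality = (1.0/1.5) × √(37/2) = 2.867, which gives 80.8% power on 72 df (plan: 80%). With R² = 0.25, 2.867/√0.75 = 3.311, which gives 90.4% (plan: 90%). 74/0.75 = 98.7, so 99, against 100 enrolled. All reproduce. No power is stated for any functional outcome.

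**2. Why the unstratified test is conservative.** With full balance on the factors, the true variance of the arm contrast is (1 − R²) times the variance the test assumes.
- Size = 2[1 − Φ(1.96/√(1 − R²))]: 0.050, 0.044 and 0.039 at R² = 0, 0.05 and 0.10.
- Power is Φ((δ − 1.96)/√(1 − R²)) unadjusted and Φ(δ/√(1 − R²) − 1.96) adjusted.
- With δ = 2.867: 82.4% vs 83.7% at R² = 0.05 (+1.3 points) and 83.1% vs 85.6% at 0.10 (+2.5).
- With δ = 0.5 × √18.5 = 2.151: 57.8% vs 59.7% (+2.0, from unrounded values) and 58.0% vs 62.1% (+4.1).

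A simple variance-reduction formula, which ignores the stratified allocation, gives +1.9 and +3.9 points near 80% power. That is too high there.

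**3. Simulation, Wilcoxon vs rank-ANCOVA** (ranks regressed on arm and both factors; stratified blocks; 10,000 to 20,000 trials per setting). Change in power, in points:

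| Setting | R² 0 | R² 0.05 | R² 0.10 |
|---|---|---|---|
| 74 analysed, power near 80% | −0.1 to +0.1 | +1.2 to +1.4 | +2.6 to +2.7 |
| 100 analysed, power near 91% | 0.0 | +0.8 | +1.5 |
| 74 analysed, power near 54% | +0.1 | +2.2 | +4.3 |
| 74 of 100 analysed, 0–21 scale, power near 70% | −0.1 to 0.0 | +1.6 to +1.9 | +3.0 to +3.8 |
| 60 of 100 analysed | −0.3 | +1.6 | +3.8 |
| Worst value for about 15% deaths | −0.1 | +2.1 | +3.6 |

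Null size on complete cases was 0.040 to 0.046 for the Wilcoxon at R² 0.05–0.10, and 0.050 to 0.052 for the rank-ANCOVA. At R² = 0, runs of 40,000 trials gave −0.1 (74 analysed) and −0.4 (60 analysed). The largest loss seen, −0.6, came from a run of only 8,000.

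**4. Under multiple imputation** (100 patients, 26 missing, 20 imputations; imputation model assumed). Power was 67.7 / 68.2 / 69.3% for the Wilcoxon and 69.0 / 70.8 / 73.5% for the rank-ANCOVA: +1.3 / +2.6 / +4.2 points. Not all of that is adjustment, since at R² = 0 the factors carry no information. A separate run of 4,000 trials split it:
- Wilcoxon null variance: 67.3 / 68.1 / 68.8%.
- Rank regression on arm only: 68.5 / 69.0 / 70.1%.
- With both factors: 68.7 / 70.4 / 72.7%.

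The variance formula alone contributes 1.2 / 0.9 / 1.3 points; the factors add 0.2 / 1.4 / 2.6.

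**5. Enrollment ADL as a covariate** (74 analysed, factor R² 0.05, assumed 0–6 scale with a ceiling). With the factors only, power is 69.6%. The three values below are for a clean baseline, proxy noise with 10% missing, and proxy noise with 20% missing.
- Correlation 0.3: 70.6 / 70.0 / 69.6%, a gain of 1.0 / 0.4 / 0.0 points.
- Correlation 0.5: 75.8 / 73.7 / 73.2%, a gain of 6.2 / 4.1 / 3.6 points.
- If neither the baseline nor the factors are prognostic, runs with a continuous baseline or an ordinal outcome lost up to 0.7 points against the Wilcoxon.
- If answers were given after the arm was known and differed between arms by 0.2 / 0.3 / 0.5 SD, adjusting would give size 0.05 / 0.06 / 0.07 at correlation 0.3 and 0.06 / 0.07 / 0.11 at 0.5.

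**The case against.** An unadjusted Wilcoxon test for non-normal secondary outcomes in a phase 2 pilot is conventional, explained and valid. The gain rests on assumed R², shift, scale and block size. Section 4.1 already allows proportional-odds models, and its wording about no covariate adjustment attaches to the Wilcoxon option, so an adjusted ordinal model would fit the existing text. Much of this stands: it is why the point is optional and the gain is given as a range. It does not remove the point, because Section 4.1 names no covariates for functional outcomes and Section 9.4.3 names only the Wilcoxon.

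The objection is also right that a rank-based effect must be defined with care. If 40% of patients sit at the ADL ceiling and the other 60% spread evenly over six scores (both assumed), Pr(tie) = 0.40² + 6 × 0.10² = 0.22. Under no effect the chance of a strictly higher score is then (1 − 0.22)/2 = 0.39, not 0.5. Ties must count one half.

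On ADL, Section 8.1 lists the survey among baseline assessments, and the shared schedule column also holds consent and demographics. A reader might infer that the survey follows allocation in this open-label trial. The documents do not say so; they leave the order unstated.

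**Conclusion.** The point holds as a small, nearly free precision gain on secondary outcomes for which no power is stated; low severity. At an assumed R² of 0.05 to 0.10 the gain is roughly 1 to 4 points: 1 to 3 near 80% power and 2 to 4 near 55 to 70%. The cost is about half a point or less if the factors are uninformative. That bound covers the two factors only; an uninformative ADL baseline can cost up to about 0.7. The proportional-odds alternative was not simulated.

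A reader might infer that omitting the factors makes the functional tests invalid, raises the false-positive rate or touches the primary result. None of these is supported: the error is toward conservatism, and Section 9.4.2 adjusts the primary model for both factors. Nor may the 80% to 90% power rise in Section 9.2 be carried over, since it depends on R² = 0.25 for all hemoglobin covariates together.

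**What to change.** - In 9.4.3, choose one method per functional outcome: a rank-ANCOVA on arm, anemia etiology and ICU admission indication as entered at randomisation, or the proportional-odds model of Section 4.1 with the same two factors. Make Sections 4.1 and 9.4.3 name the same method. A van Elteren stratified test is not an equal substitute: it lost 0.7 to 2.1 points in simulation when the factors were uninformative.
- Put arm and both factors in the imputation model. Pool the arm effect and its standard error by Rubin's rules and report it with a 95% CI.
- If the rank-ANCOVA is used, the effect is the arm coefficient divided by N. It estimates P − 0.5, where P = Pr(higher) + ½ Pr(tie) for an intervention patient against a control patient. State for each score whether higher is better.
- Use the same model in the worst-value analysis, and keep the plain Wilcoxon as a sensitivity analysis.
- For ADL at 1 and 3 months, add the enrollment score with a patient/proxy indicator only if the schedule places the survey before randomisation; otherwise leave it out. Discharge EQ-5D and PROMIS-Fatigue are post-randomisation and cannot serve as baselines.
- Settle the wording before outcomes are seen by arm. Section 6.3 leaves room for this: "all data analysts will be blinded to treatment allocation while the study is ongoing".

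The cost is SAP wording and, for the ADL option, one schedule line and a field for who answered if the form lacks one. No extra patients or visits are needed, and the Chi-square, log-rank and Gray's tests need no change.

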We anticipate up to 10% ICU mortality (despite exclusion of those not expected to survive hospitalization); such subjects will not have observed hemoglobin outcomes. We also anticipate additional post-ICU discharge mortality. In the primary analysis, we assume missing data due to death is MAR. Those with ICU mortality will have ICU discharge hemoglobin multiply imputed under the MAR assumption. Thereafter, LMMs assume additional missing data at other times are MAR. In secondary approaches to the analysis of hemoglobin, we use a worst-case imputation approach, to impute hemoglobins as the worst possible outcome following death. After imputation, if residuals are not reasonably normally distributed, a generalized linear mixed effects proportional odds model will be used or individual timepoints may be assessed by Wilcoxon rank-sum test without covariate adjustment. A similar approach using proportional odds models or Wilcoxon rank-sum test will apply to functional outcomes which are not expected to satisfy regression assumptions including normality of residuals. Similar approaches assuming MAR and MNAR will be applied to missing functional outcome data.

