## 5.2 EXCLUSION CRITERIA

An individual who meets any of the following criteria will be excluded from participation in this study:

1. IV iron or any ESA use (i.e. darbepoetin, Aranesp, erythropoietin, Epojen, Procrit, Retacrit) within 30 days of enrollment. Oral iron is permitted (e.g. oral iron supplements, multivitamin with iron)
2. Severe anemia prior to hospitalization (i.e. hemoglobin consistently  $< 9$  g/dL in the 90 days prior to admission). If hemoglobin is not available or if hemoglobin is  $\geq 9$  g/dL at any time within 90 days prior to enrollment, then this criterion is not met, and the patient may be enrolled
3. Known allergic reactions to IV iron or any EPO agent
4. Inability to complete outcome assessments (i.e. not expected to survive hospitalization, unable to make follow-up appointments, non-ambulatory status preceding hospitalization, dementia or other severe cognitive impairment, visual impairment i.e. blind or legally blind, non-English speaking)
5. Pregnancy or breastfeeding at time of enrollment given unclear safety of EPO
6. Inability to receive pharmacologic venous thromboembolic prophylaxis except in patients with acute blood loss anemia (i.e. recent surgery or gastrointestinal bleeding, extracranial bleeding)
7. Active or suspected thrombosis (i.e. DVT, pulmonary embolism, acute arterial thrombus) within 3 months except in patients with acute blood loss anemia (i.e. recent surgery, gastrointestinal bleeding, extracranial bleeding)
8. Uncontrolled sepsis (i.e. lack of definitive source control and/or  $< 48$  hours of appropriate antimicrobial therapy)
9. Having received  $\geq 10$  units of allogeneic RBCs in the 48 hours before enrollment
10. Acute coronary syndrome (STEMI or NSTEMI) or ischemic stroke within 3 months except in patients with acute blood loss anemia (i.e. recent surgery, gastrointestinal bleeding, extracranial bleeding)
11. Weight less than 40 kg
12. Concerns with study enrollment expressed by the clinical team

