
Retention: A high-level of patient follow-up (>75%) is necessary for success, including in-person evaluations for hemoglobin laboratory draws. To achieve this, we have limited the study to residents residing locally (i.e. patients that receive routine medical cares in Mayo Clinic Rochester or the regional Mayo Clinic Health System), a unique population with a high-level of community engagement in clinical research and a high-level of post-hospitalization medical cares obtained primarily at the Mayo Clinic and its affiliated regional sites. Similar studies of Olmsted County residents, including those with laboratory draws, have achieved >90% retention. Additionally, we are partnering with the Mayo Clinic ICU Rehabilitation Program (MCIRP). The MCIRP is a post-ICU clinic staffed by a physician, advanced ICU care nurse practitioner, ICU pharmacist, and occupational therapist, with the recent addition of a nurse coordinator. In the current care model, survivors of critical illness, identified through real-time electronic data "sniffers", and their family members are approached by MCIRP team members for recruitment prior to hospital discharge. Patients are evaluated within 6 months of hospital discharge with a less than 5% no-show rate for enrolled participants and greater than 90% retention for additional visits. Multi-domain functional outcomes (physical, cognitive, mental health, quality of life) are assessed at each study visit in accordance with the NHLBI-funded improveLTO Core Outcome Measure Set (<http://improvelto.com>). Of note, with COVID-19 precautions, most MCIRP visits have been moved to virtual visitations. We will work with the MCIRP to ensure appropriate follow-up of all enrolled patients. Our goal remains in-person evaluations for all study participants in an outpatient setting. Of note, all core functional outcomes can be assessed over

the phone with exception of 6MWD. *Additional* retention in this clinical trial will be facilitated through employment of published cohort retention tools for longitudinal post-hospitalization critical care outcomes research

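### The plan has no rule for a living patient who cannot perform the 6-minute walk; if the test is recorded as missing, MAR imputation supplies a walker's distance, with bias possible in either direction

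*Combined protocol and SAP*

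**What the plan says.** Section 9.4.3 sets the handling of missing functional outcomes: the primary approach takes death and dropout to be MAR, and "multiple imputation will be used to impute missing values". It then adds: "An additional analysis will consider a worst-value imputation for mortality, assigning death the worst possible outcome". No other worst-value rule is given there.

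Section 4.1 (Statistical considerations) says of the same outcomes: "Similar approaches assuming MAR and MNAR will be applied to missing functional outcome data". The only non-MAR method described in that section is worst-case imputation after death.

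For hemoglobin, section 9.4.2 states: "Dropout or non-response including skipped study visit and death represent two forms of missing data". Being alive but unable to do a test is not a category there, or anywhere else in the document. Section 7.2 asks for the reason for withdrawal from the study; no section asks for the reason a test was not done.

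The planned test is rank-based: "Analyses will use Wilcoxon rank-sum tests to compare the distribution of each outcome between groups at each timepoint" (section 9.4.3). Section 5.5 says the core functional outcomes can all be collected over "the phone with exception of 6MWD".

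**The concern.** Inability to walk is itself a functional result, and the worst one a survivor can have on this test. If it is entered as missing, the default in section 9.4.3 replaces it with a distance predicted from patients who walked. The analysis then compares the arms as if everyone could walk. Any difference between arms in the proportion able to walk drops out.

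The 6-minute walk is the most exposed outcome because it needs a visit in person. It also matters to the trial: section 2.2 names it, with activities of daily living, as a measure associated with anemia after critical illness, and functional recovery is part of the hypothesis in section 9.1. Each secondary outcome is to yield a conclusion at two-sided 0.05, meant to inform a later trial.

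**Working it through.** **The plan's own figures.** The sample-size figures concern 1-month hemoglobin only. They reproduce: 36.3, so 37 per group, for a 1.0 g/dL difference with SD 1.5 (t-test, 80.8% power at 37); 90.4% power with SD 1.5 × √0.75; and 74/0.75 = 98.7, so 99 against the stated 100. No power figure is given for any functional outcome, so none can be checked.

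**Inputs for the walk.** From the documents: 1:1 allocation, 100 enrolled, Wilcoxon test, two-sided 0.05. Assumed, because the documents give no values: distance mean 330 m, SD 110 m; correlation 0.4 with a baseline covariate; inability 5% to 25%; difference d among walkers of 0 to 50 m; 45 survivors per arm (50 × 0.90); and no other missing data.

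**Formula.** Let p0 and p1 be the proportions unable to walk in control and intervention, and w the probability that an intervention walker outdistances a control walker, w = Φ(d / (110√2)). With inability ranked at the bottom, the probability that a random intervention survivor outranks a random control survivor (ties counted half) is

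P = (1 − p0)(1 − p1)w + p0(1 − p1) + ½p0p1.

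If inability is imputed under MAR, the terms in p0 and p1 vanish and the analysis returns roughly w.

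- d = 30 m: w = Φ(30/155.6) = 0.576. d = 50 m: w = Φ(50/155.6) = 0.626.
- 25% / 10%, d = 30: 0.389 + 0.225 + 0.0125 = 0.627, against 0.576.
- 15% / 15%, d = 50: 0.452 + 0.1275 + 0.011 = 0.591, against 0.626.
- 10% / 20%, d = 30: 0.415 + 0.080 + 0.010 = 0.505, against 0.576.

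**Simulation.** 1,500 trials per scenario, imputation model with arm and baseline covariate, 20 imputations, pooled. The rejection rate at 0.05 is in brackets.

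| Unable, control / intervention | d (m) | Inability scored 0 m | MAR imputation |
|---|---|---|---|
| 15% / 15% | 0 | 0.500 (5%) | 0.499 (5%) |
| 25% / 10% | 0 | 0.569 (19%) | 0.500 (4%) |
| 25% / 10% | 30 | 0.619 (50%) | 0.574 (20%) |
| 20% / 10% | 30 | 0.600 (38%) | 0.575 (21%) |
| 10% / 5% | 30 | 0.588 (29%) | 0.576 (22%) |
| 15% / 15% | 50 | 0.592 (33%) | 0.626 (49%) |
| 10% / 20% | 0 | 0.454 (12%) | 0.497 (6%) |
| 10% / 20% | 30 | 0.509 (5%) | 0.575 (20%) |

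The simulated values lie within 0.008 of the formula. The small gap arises because the unable patients also have lower baseline values, so the remaining walkers are slightly selected.

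**The case against.** **The text is silent rather than wrong.** A reader might infer that section 9.4.3 orders a distance to be imputed for every patient who cannot walk. It does not say so. It names death and dropout, then missing values, and no section says how an attending patient who cannot walk is recorded. Staff could enter 0 m. This stands, and it limits the point to what could happen. It does not remove it: without a rule, the same patient may be 0 m or missing depending on who fills in the form.

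**The MNAR sentence in section 4.1.** It shows that the planners did not rely on MAR alone. But it names no method for survivors, so it does not settle the matter.

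**Direction.** A reader might infer that imputation always pulls the result toward no difference. The table contradicts that. With equal inability and a benefit among walkers, the estimate moves away from no difference; with more inability in the intervention arm and a benefit among walkers, it does so again. With equal inability and no benefit among walkers there is no bias.

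**Scope.** Section 5.2 excludes patients with "non-ambulatory status preceding hospitalization, dementia or other severe cognitive impairment", which limits how many will be unable later, although new inability after intensive care remains possible. Loss of walking can still show in the activities of daily living survey and EQ-5D, both obtainable by phone. The imputation model is not specified and could use those measures. It would still predict a walking distance unless inability itself is coded. The case for MoCA-BLIND is weaker: it can be done by phone, and a physical barrier to testing is not a cognitive deficit.

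**Estimand.** Scoring inability as 0 m is a choice of what to estimate. The all-MAR analysis answers a different question, the distance had everyone been able to walk. That supports keeping it as a sensitivity analysis.

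**Conclusion.** The concern holds in limited form. The plan does not separate being alive but unable to walk from other missing values, its stated default is MAR imputation, and its MNAR promise has no content for survivors. If inability is recorded as missing, its contribution is lost from the 6-minute walk comparison. The result moves toward no difference when the intervention reduces inability, as when 0.619 becomes 0.574 and power falls from 50% to 20%. It moves away from no difference when inability is equal or more common in the intervention arm and walkers benefit, as when 0.592 becomes 0.626 or 0.509 becomes 0.575. Extra inability in the intervention arm with no benefit among walkers is simply hidden (0.454 becomes 0.497).

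No single size should be quoted as the effect. Every distance, SD and inability rate above is assumed, and the loss shrinks as inability becomes rarer (0.588 to 0.576 at 10% / 5%). A figure in metres would be even more dependent on its inputs, because setting walkers equal in both arms forces the MAR answer to about zero. These are secondary outcomes in a phase 2 pilot, so the change is advisable rather than essential.

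**What to change.** 1. Add one case report form field giving the reason for each 6-minute walk not done, assigned by the blinded outcome assessor that section 4.1 already provides for.
2. In section 9.4.3, state: *A participant who is alive and documented as physically unable to walk is scored 0 m. Multiple imputation is used only for values missing for other reasons, including inability to travel without documented inability to walk.* The planned Wilcoxon test takes 0 m as a tied bottom rank among survivors.
3. State that in the death-as-worst analysis 0 m ranks above death.
4. Report the all-MAR analysis as a sensitivity analysis, and make the MNAR sentence in section 4.1 refer to these rules.
5. For MoCA-BLIND, limit any worst-score rule to documented cognitive incapacity. Do not assign the lowest score for physical incapacity.

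The cost is one form field and a few sentences of plan text, with no change to the test or the sample size. The downside is some judgement in coding the reason, which blinded assignment keeps from depending on arm.
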